**Model Results Presentation**

- Treatment group mean annual exacerbation rates, treatment rate ratios and associated 95% confidence intervals (CI) and p-values will be presented. The treatment rate ratios and associated 95% CIs will also be presented graphically.
- Percentage reduction in annual exacerbation rates and associated 95% CIs will also be presented.

**Endpoint / Variables**

- Time to first moderate/severe exacerbations
- Time to first severe exacerbations

**Model Specification**

- Cox's proportional hazards model
- All asthma exacerbations observed during the study (on- or post-treatment) will be used in the analyses
- Participants who prematurely discontinue from the study will be censored at the date of their EW visit + 1 day.
- Terms in the model:
  - Response: time to first moderate/severe asthma exacerbation during the study (both on- and post-treatment) or time to first severe asthma exacerbation during the study (both on- and post-treatment)
  - Covariates:
    - Categorical: treatment group, sex, region, severe asthma exacerbations in the previous year (0,  $\geq 1$ ).
    - Continuous: age
- The ‘exact’ method will be used for handling ties. If the analysis will not run using the ‘exact’ method, then the ‘Efron’ method for handling ties will be used instead.

**Model Checking & Diagnostics**

- The proportional hazards assumption will be examined by obtaining the Kaplan-Meier estimates of the survival function  $S(t)$  over time separately for each treatment group. Under the assumption of proportional hazards between the treatment groups,  $\ln\{-\ln[S(t)]\}$  for two

groups should be parallel to each other and the distance between them constant. If the curves are approximately parallel, then the proportional hazards assumption is not violated. If these curves cross each other or diverge greatly from the assumption of parallel lines, then the assumption is not met.

**Model Results Presentation**

- Hazard ratios for pairwise treatment comparisons with associated 95% CIs and p-values will be presented.
- Kaplan-Meier survivor functions will be obtained for each treatment group using PROC LIFETEST with a TIME statement.
- A listing of exacerbations where the onset occurs within 14 days of study withdrawal or treatment discontinuation will also be produced.

Additionally, descriptive statistics, including all on- and post-treatment data, for the following parameters will be presented:

- Clinic FVC (L) at Baseline, Week 4, Week 12 and Week 24.
- Clinic FEV/FVC ratio at Baseline, Week 4, Week 12 and Week 24
- Clinic FEV1 percent predicted of normal (%) at Baseline, Week 4, Week 12 and Week 24.
- Global Assessment of Severity and Response to Treatment at Baseline (Severity only), Week 4, Week 12 and Week 24

All baseline data will be presented in separate tables in order to present both by treatment group and for the overall analysis population.

## 8. SAFETY ANALYSES

The safety analyses will be based on the ITT population including all data collected during the study. Participants will be analyzed according to the treatment they were randomized to. On-treatment safety data collected at scheduled clinic visits will be summarized and analyzed by treatment and by visit, unless otherwise specified. Run-in adverse events, on-treatment adverse events and post-treatment adverse events will be summarized separately.

**Table 5** provides an overview of the planned analyses, with further details of data displays being presented in [Appendix 9: List of Data Displays](#).

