### 4. ANALYSIS POPULATIONS

Population	Definition / Criteria	Analyses Evaluated
All Subjects Enrolled	

This population will comprise all participants for whom a record exists on the study database, including pre-screened participants that sign the informed consent document but do not complete a Visit 1 (screening) procedure (i.e., pre-screening failures), or participants that complete at least one Visit 1 procedure but do not enter the run-in period (i.e., screening failures).

	

Study Population

All Subjects Screened	

This population contains all participants that complete at least one Visit 1 (Screening) procedure

	

Study Population

Safety

Randomized	

This population will comprise of all participants who were randomized (i.e. were assigned a randomization number)

	

Study population

Intent-to-Treat (ITT)	

This population will comprise all randomized participants, excluding those who were randomized in error. A participant who is recorded as a screen failure or run-in failure but is randomized and does not receive a dose of study treatment, is considered to be randomized

	

Study population

Efficacy

Safety

Population	Definition / Criteria	Analyses Evaluated
	in error. This population will be based on the treatment the participant was randomized to receive.	

Refer to [Appendix 9](#) : List of Data Displays which details the population used for each display.

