### 5.2. Baseline Definitions

In general, the baseline value is the last assessment value, including unscheduled assessments (where stated), prior to randomized treatment start for the efficacy endpoints based on assessments at clinic visits, unless otherwise specified, and the average value over the last 14 days prior to randomized treatment start during the run-in period for the efficacy endpoints based on participants' diary data.

If time is not collected, Day 1 clinic assessments (or Day 1 AM diary assessments) are assumed to be taken prior to first dose and used in the derivation for baseline

Parameter	Study Assessments Considered as Baseline		Baseline Used in Data Display
	Screening	Day 1 (Pre-Dose)	
Efficacy: Clinic Spirometry			
Trough FEV 1 , FEV 1 3h post-dose, FVC, FEV 1 /FVC Ratio, FEV 1 % predicted		X	Day 1 (pre-dose)

Parameter	Study Assessments Considered as Baseline		Baseline Used in Data Display
	Screening	Day 1 (Pre-Dose)	
Efficacy: Questionnaires			
ACQ-5, SGRQ, AQLQ, Global Assessment of Severity		X	Day 1
Efficacy: Diary Assessments			
	Baseline Period		
Home trough FEV 1 , AM PEF	Last 14 AM assessments during the run-in period, including AM assessment on the day of first randomized treatment (i.e., treatment start date per protocol)		Baseline
PM FEV 1 , PM PEF	Last 14 PM assessments immediately preceding the day of first randomized treatment during the run-in period		Baseline
Daily rescue medication use	Last 14 days during the run-in period, including AM assessments on the day of first randomized treatment (i.e., treatment start date per protocol).		Baseline
E-RS total score	Last 14 PM assessments immediately preceding first randomized treatment during the run-in period		Baseline
Safety			
ECGs	X		Screening
Vital signs		X	Day 1

Unless otherwise stated, if baseline data is missing no derivation will be performed and baseline will be set to missing.

For participants that did not receive any randomized study treatment, baseline is defined as the value from the protocol scheduled baseline visit. Unscheduled visits will not be considered.

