## 10.4. Appendix 4: Study Phases

### 10.4.1. Study Phases

Study phases for assessments scheduled at a set time will be defined according to the planned relative time of the assessment.

Any events/assessments for participants not in the ITT population will be assigned a Pre-treatment phase.

For all events and assessments, the study phases will be defined as follows:

Study Phase	Definition
Screening/Run-In period	Visit 1 date ≤ Assessment Date/Time < Date of randomization or randomized treatment start date, whichever is later.
On-Treatment during the Study	Randomized Treatment Start Date ≤ Event Onset Date or Assessment Date/Time ≤ Study Treatment Stop Date +1 day or any assessment with a missing or partial date unless there is evidence it was not on-treatment
Post-Treatment during the Study*	Randomized Treatment Stop Date +1 < Event Onset Date or Assessment Date/Time ≤ Last Scheduled Clinic Visit (i.e., Visit 5 (EOS Visit) or Early Withdrawal [EW] Visit) Note: if any participant does not receive a dose of randomized treatment then all post baseline data prior to early withdrawal or EOS visit is considered as post-treatment.
Post-Study	Event Onset Date > Last Scheduled Clinic Visit (i.e., Visit 5 (EOS Visit) or Early Withdrawal Visit) +1 day Note, for participants who continue in the study after IP discontinuation (i.e. where treatment discontinuation date < Visit 5 (EOS visit) date or EW visit date), the rule will be: Event Onset Date > Last Scheduled Clinic Visit (i.e. Visit 5 (EOS Visit) or EW Visit)

\*Only applicable for participants who continue in the study after IP discontinuation

Classification of a concomitant medication into study phases (pre-study period [at study entry], screening/run-in period, on-treatment during the study, post-treatment during the study, or post-study) will be made with reference to the study phase as defined above. A medication will be classified into every period in which it was taken. For medications with partial start and stop dates, the medication will be classified into every period in which it could have been taken.

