**Planned and Actual Treatment**

For participants who received the correct treatment throughout the study, the actual treatment will be the same as the planned treatment. For participants who received an incorrect treatment, the actual treatment will be derived as follows:

- If the number of doses on an incorrect treatment is less than the number of doses on the planned treatment then the actual treatment is assigned as planned treatment.
- If the number of doses on an incorrect treatment is greater than the number of doses on the planned treatment then the actual treatment is assigned as the incorrect treatment.
- If the number of doses on an incorrect treatment and planned treatment are the same, the actual treatment is assigned as the treatment with the highest UMEC dose.

Note: If any container (correct or incorrect) was dispensed and not returned, such that it is not possible to ascertain whether or not any doses were taken from the incorrect container, it will be assumed that the participant took all 30 possible doses from this container.

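### Safety is summarised in the ITT population by randomised arm although treatment actually received is derived; grouping dosed participants by that variable would be a cheap, low-severity improvement

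*SAP*

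**What the plan says.** Section 8 sets the analysis set and the grouping for safety: "The safety analyses will be based on the ITT population including all data collected during the study", and "Participants will be analyzed according to the treatment they were randomized to". All safety tables in Section 10.9.8 (3.1 to 3.54) name ITT as their population. Section 4 defines no population that requires a dose or groups by treatment received.

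Section 4 defines ITT without a dosing condition: "This population will comprise all randomized participants, excluding those who were randomized in error". An undosed participant counts as randomised in error only if also recorded as a failure before randomisation: "A participant who is recorded as a screen failure or run-in failure but is randomized and does not receive a dose of study treatment". Other undosed participants stay in, and the SAP provides for them twice. Section 5.2 gives them a baseline: "For participants that did not receive any randomized study treatment, baseline is defined as the value from the protocol scheduled baseline visit". Section 10.4.1 puts their later data in the post-treatment phase, in a note that begins "if any participant does not receive a dose of randomized treatment then all post baseline data".

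Section 10.6.1 (Planned and Actual Treatment) contains the derivation: "For participants who received an incorrect treatment, the actual treatment will be derived as follows". The majority of doses decides, and ties go to the highest UMEC dose. The variable serves Listing 5 (randomised and actual treatments). Listing 6 covers misallocations, and Listing 18 gives the adverse events of those who received an incorrect treatment. Section 10.5.2 adds that ad hoc displays by actual treatment may be made for individual participants.

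**The concern.** Section 2.2 states the safety objective as each UMEC dose compared with placebo. If UMEC raises a risk, leaving a placebo-randomised participant who mainly inhaled UMEC in the placebo column, or the reverse, pulls the two columns together. For a safety comparison that is the less cautious direction. The variable that would place the participant correctly is already planned, but it does not reach the adverse event, AESI, MACE, ECG or vital-sign tables.

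Undosed participants raise a separate and smaller matter. Under the phase rule they cannot have an on-treatment event, yet they count in the denominator of the on-treatment percentages.

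**Working it through.** The SAP states no figure to reproduce. The check compares the rules and then sizes the effect under stated assumptions.

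**Inputs**
- Randomised by country (Section 5.4): 174 + 69 + 21 + 114 + 58 = 436. With 1:1:1 allocation, 436/3 = 145.3, so about 145 per arm.
- Double-blind treatment: once daily for 24 weeks (Section 2.3), 24 × 7 = 168 doses. A container holds 30 (Section 10.6.1).
- Assumed, not in the SAP: event risks of 8% on UMEC and 2% on placebo; 1 to 10 misallocated or undosed participants per arm; percentage denominators equal to ITT arm totals.

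**1. Who is reclassified.** The derivation moves a participant in this case: "If the number of doses on an incorrect treatment is greater than the number of doses on the planned treatment" (or on a tie, by the tie rule). For a completer, one wrong container is 30 against 138 doses and two are 60 against 108, so neither changes the arm. Three are 90 against 78, which does. A single wrong container can suffice only for someone who stops early.

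**2. Placebo-UMEC misallocation.** With m placebo-randomised participants mainly on UMEC:

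placebo percentage shown = [(145 − m) × 2% + m × 8%] / 145; difference shown = 8% − that value.

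For m = 1: (144 × 0.02 + 1 × 0.08)/145 = 2.96/145 = 2.04%, difference 5.96 points.

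If m participants are misallocated in each direction, the difference shown is 6.0 × (1 − 2m/145).

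| m | One direction | Both directions |
|---|---|---|
| 0 | 6.00 | 6.00 |
| 1 | 5.96 | 5.92 |
| 5 | 5.79 | 5.59 |
| 10 | 5.59 | 5.17 |

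**3. Undosed participants.** With u undosed, percentage shown = true percentage among the dosed × (145 − u)/145.

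| u | True 10% | True 2% |
|---|---|---|
| 1 | 9.93% | 1.99% |
| 5 | 9.66% | 1.93% |
| 10 | 9.31% | 1.86% |

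The relative understatement runs from 1/145 = 0.7% to 10/145 = 6.9%.

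**4. Displays not touched by undosed participants.** Section 10.6.4 divides event counts by total exposure, and an undosed participant adds none, so the rates per thousand person-years are unaffected. Such a participant also has no on-treatment ECG or vital-sign value, so those summaries are unaffected too.

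**The case against.** As-randomised reporting is an explicit choice, stated alike in Sections 4, 8 and 10.5.2, and the actual-treatment variable has its own planned use in Listing 5. A reader might infer that the SAP contradicts itself. It does not.

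The safeguards are real. Under Section 10.1 an incorrect container is an important protocol deviation, and the contents are identified and checked before database freeze. Listings 5, 6 and 18 make the cases visible. This stands, but a listing does not change the tables from which arms are compared.

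The derivation would move few people, as step 1 shows. When it does move someone, events that occurred on the minority treatment move too, so grouping by actual treatment is not exact either. Both points stand and limit the gain.

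Two stronger readings are tempting. One is that each misallocated participant shifts incidence by 0.7 percentage points (1/145 = 0.69%). That holds only if this participant has the event in question. The expected shift in the example is 0.04 points. The other is that undosed participants hide a UMEC signal. They lower the percentage in whichever arm they sit, so undosed placebo participants would widen the difference. Nor do swaps between the two UMEC doses dilute the placebo arm; they blur the comparison of doses.

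The undosed group should also be small. Those recorded as screen or run-in failures are excluded, and the first double-blind dose is scheduled at the randomisation visit (Section 10.2.1).

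**Conclusion.** The point holds as a low-severity weakness of specification. Safety tables are fixed to the randomised arm in a population that can include undosed participants, while the variable needed to group by treatment received is already derived.

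Only misallocation between placebo and UMEC attenuates the main safety contrast. Under the assumed 8% and 2% risks the loss is 0.04 points for one placebo-randomised UMEC taker and 0.41 points for ten (6.00 − 5.59). The undosed effect is confined to percentage tables and has no fixed direction. If there are no such participants, both effects are nil. The SAP gives neither count, and the existence of listings for misallocation should not be read as evidence that any occurred.

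**What to change.** Add to Section 4 a safety population of participants with at least one dose of double-blind treatment, grouped by the actual treatment from Section 10.6.1. Use it in Section 8 and in Section 10.9.8 for on-treatment exposure, adverse events, AESIs, MACE, ECG and vital signs. Keep efficacy in ITT by randomised arm. Run-in and post-treatment summaries can stay in ITT, so that events of undosed participants remain reported. Record the change in Section 2.1.

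If the sponsor prefers to keep the present rule, the minimum is a pre-specified as-treated repeat of the key AE, SAE, AESI and MACE tables. It would be triggered if any ITT participant is undosed or has an actual treatment different from the randomised one. This would replace the optional ad hoc displays of Section 10.5.2.

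The cost is SAP wording plus a change of treatment variable and population flag in the safety programs. The one downside is that safety and efficacy column totals may differ by a few participants, which a footnote can explain.

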**Table 5 Overview of Planned Safety Analyses**

	Absolute				Change from Baseline			
	Summary		Individual		Summary		Individual	
	T	F	F	L	T	F	F	L
Exposure								
Summary of Exposure During the Run-in Period	Y			Y				
Summary of Treatment Exposure	Y			Y				
Summary of Post-Treatment Duration on Study	Y			Y				
Adverse Events (AEs)								
Relationship of AE System Organ Class, Preferred Term and Verbatim Text				Y				
Pre-treatment AEs								
AEs during the run-in period	Y			Y				
Overview of On-treatment AEs								
Overview of On-Treatment AEs	Y							
Overview of On-Treatment AEs during the study adjusted for exposure (per thousand person-years)	Y							
AEs								
On-Treatment AEs	Y			Y				
On-treatment AEs during the study adjusted for exposure (per thousand person-years)	Y							

	Absolute				Change from Baseline			
	Summary		Individual		Summary		Individual	
	T	F	F	L	T	F	F	L
Post-Treatment AEs	Y			Y				
Post-Study AEs	Y							
Drug-related AEs								
On-Treatment Drug-Related AEs	Y							
On-Treatment Drug-related AEs during the study adjusted for exposure (per thousand person-years)	Y							
Post-Treatment Drug-Related AEs	Y							
SAEs								
On-Treatment SAEs	Y							
On-Treatment SAEs adjusted for exposure (per thousand person-years)	Y							
On-Treatment Fatal SAEs				Y				
Post-Treatment SAEs	Y							
Post-Treatment Fatal SAEs				Y				
Post-Study SAEs	Y							
Drug-related SAE								
On-Treatment Drug-Related SAEs	Y							
On-treatment Drug related SAEs adjusted for exposure (per thousand person-years)	Y							
On-Treatment Drug-Related Fatal SAEs				Y				
AEs leading to Withdrawal								
On-Treatment AEs Leading to Permanent Discontinuation of Study Drug or Withdrawal from Study	Y			Y				
Post-Treatment AEs Leading to Withdrawal from Study	Y			Y				
AEs of Special Interest								
On-Treatment AEs of Special Interest	Y			Y				
On-treatment AEs of	Y							

	Absolute				Change from Baseline			
	Summary		Individual		Summary		Individual	
	T	F	F	L	T	F	F	L
Special Interest adjusted for exposure (per thousand person-years)								
On-Treatment SAEs of Special Interest	Y			Y				
On-treatment SAEs of Special Interest adjusted for exposure (per thousand person-years)	Y							
Post-Treatment AEs of Special Interest	Y							
Post Treatment SAEs of Special Interest	Y							
Common AEs								
Common on-treatment AEs (1% or More of Subjects in Any Treatment Group)	Y							
Common on-treatment AEs (3% or More of Subjects in Any Treatment Group)	Y							
10 Most Frequent On-treatment Adverse Events in Each Treatment Group	Y							
Subgroup analyses								
On-Treatment AEs by Age Subgroup	Y							
On-Treatment AEs by Gender	Y							
On-Treatment AEs by Race	Y							
On-Treatment AEs by Region	Y							
Subject numbers								
Subject Numbers for Individual on-treatment AEs				Y				
Subject Numbers for on-treatment AEs of Special Interest				Y				

	Absolute				Change from Baseline			
	Summary		Individual		Summary		Individual	
	T	F	F	L	T	F	F	L
MACE								
On-Treatment Major Adverse Cardiac Events (Narrow Definition)	Y			Y				
On-Treatment Major Adverse Cardiac Events (Broad Definition)	Y			Y				
On-Treatment Major Adverse Cardiac Events (Narrow Definition) adjusted for exposure (per thousand person-years)	Y							
On-Treatment Major Adverse Cardiac Events (Broad Definition) adjusted for exposure (per thousand person-years)	Y							
Pneumonia and Radiography (Chest X-Rays)								
Summary of On-Treatment Pneumonia	Y			Y				
Liver Events								
Medical conditions for subjects with liver stopping events				Y				
Liver Event Results and Time of Event Relative to Treatment				Y				
Liver Event Substance Use				Y				
Liver Event Information for RUCAM Score				Y				
Liver Biopsy Details				Y				
Liver Imaging Details				Y				

	Absolute				Change from Baseline			
	Summary		Individual		Summary		Individual	
	T	F	F	L	T	F	F	L
Laboratory Parameters								
Chemistry Data Outside the Normal Range				Y				
Hematology Data Outside the Normal Range				Y				
Vital Signs								
Vital Sign Data (Pulse Rate, Sys BP, Dia BP)	Y			Y	Y			
12-Lead ECGs								
ECG Values	Y				Y			Y
ECG Findings	Y			Y				
ECG Findings Shifts from Baseline	Y							
QTcF Categories	Y				Y			
ECG Abnormalities	Y			Y				Y
Maximum Post-Baseline QTcF	Y	Y			Y	Y		

**NOTES:**

T = Table, F = Figure, L = Listing, Y = Yes display generated.

- Summary = Represents TF related to any summaries (i.e. descriptive statistics) of the observed raw data.

- Individual = Represents FL related to any displays of individual participant observed raw data.

1. Statistical analysis also performed for change from baseline in vital signs (pulse rate, SBP, DBP) and ECG parameters (PR interval and QTc(F) interval)

## 8.1. Extent of Exposure

Exposure will be summarized for the ITT population.

Exposure to open label FF 100mcg during the run-in period will be summarized and presented in the following categories:  $\geq 1$  day,  $\geq 1$  week,  $\geq 2$  weeks.

Overall extent of exposure to open label FF 100mcg and to double blind study treatment during the randomized treatment period will be summarized in increments of 4 weeks for  $\geq 1$  day,  $\geq 4$  weeks,  $\geq 8$  weeks,  $\geq 12$  weeks,  $\geq 16$  weeks,  $\geq 20$  weeks,  $\geq 24$  weeks. The category 24 weeks (-5/+2 days) will also be presented to capture the number of participants completing treatment per protocol, including permitted visit windows.

Post-treatment duration in study will also be summarized using the categories 0 weeks (i.e. participants who discontinued IP and withdrew from the study at the same time),  $>0$  to 4 weeks,  $>4$  to 12 weeks and  $>12$  weeks for participants who prematurely discontinued from study treatment. The number of days of post-treatment data will also be summarized for all participants with at least one day of post-treatment data.

